### **Statistical Methods:**

Detailed methodology for summary and statistical analyses of the data collected in Parts 3 and 4 this study will be documented in a statistical analysis plan, which will be maintained by the sponsor. This document may modify the plans outlined in the protocol; however, any major modifications will also be reflected in a protocol amendment and documented in the clinical study report.

### Clinical Endpoints

Categorical variables will be summarized using counts and percentages, while continuous variables will be summarized using the mean, median, standard deviation, minimum, maximum, and number of observations. The frequency of AEs will be tabulated. Baseline, end-of-study, and change from baseline clinical laboratories, vital signs, ECG and imaging data will be summarized. Descriptive statistics will be computed for safety parameters as appropriate. Further statistical evaluations may be applied for select endpoints, if warranted.

### Efficacy Endpoints

[figure not shown]
Tumor response and disease progression will be evaluated by the independent central review (ICR) for the Part 4 primary endpoint and the Part 3 secondary endpoint; and by the investigator for secondary efficacy endpoints (Parts 3 and 4) according to the Lugano Classification for Lymphoma ([Cheson, 2014](#)).

All subjects who receive at least 1 dose of study medication will be included in the full analysis set (FAS) for the efficacy analysis.

The efficacy analysis will include the ORR, DOR, and DCR at the Final Study Assessment Visit. Subjects who have not progressed at the time of analysis will be censored at the date of their last tumor assessment. Progression-free survival and OS will also be presented using Kaplan-Meier techniques.

The overall response rate (ORR) and DOR will be descriptively summarized; exact 95% confidence intervals (CI) will be produced.

## 1.2 Study Schema

### 1.3 Schedule of Activities (SoA)

**Table 1-1. Schedule of Activities**

	SCR a	Treatment Period (21-day Cycles) b								EoT d	STFU e	LTFU f	Notes
		D1	D3	D5	D8	D10	D12	D15 c	D16-21				
General and Safety Assessments													
Informed consent	X												
Eligibility criteria	X												
Demography	X												
Physical exam	X	X								X			Complete physical exam at screening and EoT. Abbreviated exam D1 of every cycle. See Section 8.4.4 for details.
Height	X												
Weight	X	X	X	X	X	X	X	(X)		X	X		Body weight measured before the start of treatment on C1D1 will be used to calculate the MT-3724 dose in all subsequent cycles. The dose must be re-calculated when the body weight has changed by $\geq 10\%$ from the baseline value; or according to institutional policies should they require adjustment for any change in body weight. (X): Collected only if weekly dosing is implemented.
BMI	X												
Medical history	X												Illnesses that occurred at any time before the start of screening that, in the investigator's opinion, could increase the risk to subject and/or influence the study endpoints should be captured in the medical history as prior illnesses. Illnesses that are active at the time of informed consent should be captured in the medical history as concomitant illnesses.
NHL assessment	X												Initial diagnosis : include the type, histology, staging (Ann Arbor Classification-Cotswold Modification) and grading according to International Prognostic Index (IPI) for NHL At time of relapse : IPI and time to progression after first line of therapy (captured as date of first relapse/progression) Current status : additionally collect the genetic mutational status (eg, MYC, BCL2, and BCL6 rearrangement / overexpression) and molecular subtype (GCB vs ABC) (if available).

**Table 1-1. Schedule of Activities**

	SCR a	Treatment Period (21-day Cycles) b								EOI d	STFU e	LTFU f	Notes
		D1	D3	D5	D8	D10	D12	D15 c	D16-21				
Prior medication	X												Any medication (prescription, OTC, and supplements) used within 4 weeks prior to the start of treatment.
Prior systemic NHL therapy (including SCT and CAR-T)	X												The start and stop date of each individual agent / regimen and outcome should be recorded. The date of the last CD20-based therapy should also be documented in the eCRF.
Prior NHL radiotherapy	X												
NYHA	X (X)									X			Only applicable to subjects with heart failure. (X): Only collected D1 every 7 th cycle
ECOG	X X									X			
TriPLICATE 12-lead ECG g	X (X)						(X)			X			Should be obtained as 3 standard ECGs recorded in close succession and not more than 2 minutes apart. The subject must rest quietly in supine or semi-recumbent position for at least 5 minutes before the first ECG and during the assessment. (X): Collected: 

• C1D1: predose, within 10 min before EOI, and 2.0 (<math>\pm</math> 10 min) after EOI

• C1D12: predose and 2.0 h (<math>\pm</math> 10 min) after EOI

Vital signs (BP, HR, RR, body temperature) g	X X X X X X X (X)									X X			Should be measured after at least 5 minutes of quiet rest in a sitting or semi-recumbent position. Collect VS at the following times on dosing days ( $\pm$ 10 min): 

• predose (any time before start of infusion)

• 0.5, 1, 2 hours after start of infusion

• C1D1: also collect 3 and 4 hours after start of infusion

 (X): Collected only if weekly dosing is implemented.
LVEF	X												ECHO or MUGA performed within 6 months before screening and at least 28 days after the last cancer therapy is acceptable provided the subject has not received any potentially cardiotoxic agents since then.
AE review	(X) X X X X X X X X X X X												(X): Events which occur during screening that are related to a protocol screening procedure should be reported as AEs.
Concomitant medication review		X X X X X X X X X X X											

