## 3.2 Part 4 Objectives and Endpoints

OBJECTIVES	ENDPOINTS
Primary	

 
To determine the efficacy of MT-3724 as monotherapy in subjects with relapsed or refractory DLBCL based on the ORR by the Lugano Classification for Lymphoma (Cheson, 2014)
 
	
 
overall response rate is defined as the proportion of subjects with either a CR or a PR as determined by independent, blinded central review
 

Key Secondary	

 
To determine additional measures of efficacy of MT-3724 as monotherapy in subjects with relapsed or refractory DLBCL
 
	
 
Duration of tumor response, defined as time from initial documentation of tumor response (complete response [CR] or partial response [PR]) to disease progression
 

Secondary	

 
To determine the safety of MT-3724 as monotherapy in subjects with relapsed or refractory DLBCL
 
	
 
adverse events
 
laboratory abnormalities
 
vital signs
 

 
To evaluate the effect of MT-3724 on the QT/QTc interval in subjects with relapsed or refractory DLBCL
 
	
 
electrocardiograms (ECGs)
 
adverse events suggestive of cardiotoxicity
 

 
To determine additional measures of efficacy of MT-3724 as monotherapy in subjects with relapsed or refractory DLBCL
 
	
 
overall response rate, defined as the proportion of subjects with either a CR or a PR as determined by investigator assessment
 
disease control rate (DCR), defined as proportion of subjects who have achieved CR, PR and SD (defined as SD for 6 months or longer)
 
progression-free survival (PFS), defined as the time from study enrollment to the earliest date of disease progression or death from any cause
 
overall survival (OS), defined as the time from study enrollment to death from any cause
 

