### **Cohort 1:**

The starting MT-3724 dose for each subject will be 10 µg/kg for the first 2 doses (D1, D3) and then increased to 25 µg/kg for the remaining doses (D5, D8, D10, D12) of the first 21-day cycle and all doses of Cycle 2 (D1, D3, D5, D8, D10, D12). Dosing will then continue at 25 µg/kg weekly (D1, D8, D15), beginning with Cycle 3 ([Table 6-1](#)).

If fewer than 2/6 subjects have a DLT in Cohort 1, then the study will proceed to Cohort 2. If 2 or more subjects have a DLT in Cohort 1, the study will be stopped.

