### **Cohort 2:**

The starting MT-3724 dose in each subject will be 10 µg/kg for the first 2 doses (D1, D3). The dose will then be increased to 25 µg/kg for 2 doses (D5, D8) and then the dose will be increased to 50 µg/kg for the remaining doses (D10, D12) of the first 21-day cycle and all doses of Cycle 2. Dosing will then continue at 50 µg/kg weekly (D1, D8, D15) beginning with Cycle 3 ([Table 6-1](#)).

If fewer than 2/6 subjects have a DLT in Cohort 2, then the study will continue to Part 4 using the Cohort 2 dose and schedule. If 2 / 6 subjects experience a DLT in Cohort 2, the study will continue to Part 4 using the Cohort 1 dose and schedule.

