##### **6.1.1.3 Dose Schedule**

All doses of MT-3724 will be administered as IV infusion over 1 hour (window = 54 to 75 minutes) in a 21-day cycle according to the schedule specified in each cohort ([Table 6-1](#)).

NOTE: Each dose of MT-3724 must be preceded by premedication administered within 60 minutes before the start of each infusion (see [Section 6.1.2](#))

All doses should be administered within the first 16 days of the 21-day cycle. For Cycle 1 and 2 doses are preferably administered on Days 1, 3, 5, 8, 10, and 12 ( $\pm 1$  d). For Cycle 3 and later doses are preferably administered on Days 1, 8, and 15. All cycles should use the following guidelines:

- The first 3 doses of Cycle 1 must be administered at least 2 days (approximately 48 hours) apart.
- All subsequent doses must be at least 20 hours apart (more than 5 half-lives of MT-3724 in serum), and must not be administered on more than 2 consecutive days.

The first dose of the first cycle will require approximately 5 hours in the clinic which include approximately 4 hours of post-dose safety assessments. Subsequent doses will require approximately 3 hours in the clinic which include approximately 2 hours of safety assessments post-dose (see also [Section 1.3, Schedule of Activities \(SoA\)](#)).

No more than 14 days should elapse between cycles. If more than 14 days elapse, the investigator must consult with the medical monitor before initiating the next cycle of treatment. Refer to [Section 6.2](#) for dose modification guidelines and management of toxicities.

Treatment will continue until death, disease progression, unacceptable toxicity, withdrawal of consent, or another reason for withdrawal, or until study discontinuation.

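### Under step-up dosing no scheduled ECG falls near the full-dose peak, which weakens the Part 4 QT/QTc objective; moving one triplicate to Cycle 1 Day 12 would repair this

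*Protocol*

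**What the plan says.** Protocol Section 3.2 gives Part 4 this secondary objective: "To evaluate the effect of MT-3724 on the QT/QTc interval in subjects with relapsed or refractory DLBCL". Its endpoints are ECGs and "adverse events suggestive of cardiotoxicity". No QTc threshold, precision target or exposure level is attached to it.

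Table 1-1 times the on-treatment triplicate ECGs in its notes column. The first entry is "C1D1: predose, within 10 min before EOI, and 2.0" after end of infusion (I read the last figure as hours). The second is "C1D12: predose and 2.0 h" after end of infusion. The next scheduled ECG is at the End of Treatment visit, up to 14 days after the last dose. Other ECGs are prompted by an in-clinic adverse event, where clinically indicated (Section 8.4.8).

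Section 6.1.1.2 sets the doses. Cohort 1 receives 10 µg/kg "for the first 2 doses (D1, D3) and then increased to 25" µg/kg, so Day 12 is at 25 µg/kg. Cohort 2 also receives 10 µg/kg "for the first 2 doses (D1, D3"), and reaches 50 µg/kg "for the remaining doses (D10, D12) of the first 21-day cycle". Part 4 adopts whichever of these regimens Part 3 supports.

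Table 1-2 takes Part 4 PK samples on Cycle 1 Day 12 before the dose, 10 minutes before end of infusion, and 5 minutes and 2 hours after it. Day 1 of later cycles also has a sample 10 minutes before end of infusion.

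**The concern.** With a one-hour infusion, the peak is expected at about the end of infusion. The only ECG scheduled there falls on the starter dose. On the one ECG day at full dose, the post-dose recording comes two hours later. Peak concentration at full dose is therefore measured by PK with no ECG beside it, on Day 12 and again on Day 1 of later cycles.

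Under flat dosing at 50 µg/kg from Day 1, the regimen Section 4.1.1 describes as preceding the adjustment, an end-of-infusion ECG on Day 1 would have been a full-dose reading. Step-up dosing changes what that time point measures.

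At stake is the reach of the QT/QTc result. If an effect follows concentration closely, it would be largest at an exposure where Part 4 takes no scheduled ECG, and the trial could describe it there only by extrapolation.

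**Working it through.** The plan gives no figure of its own for the QT/QTc objective, so there is none to reproduce. The sized figure in Part 4, the power of the response-rate rule, is not involved.

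**Inputs**
- Dose on Cycle 1 Day 1: 10 µg/kg in both cohorts. Dose on Day 12: 25 µg/kg (Cohort 1) or 50 µg/kg (Cohort 2). Source: Table 6-1.
- Infusion length: 1 h, allowed window 54 to 75 minutes. Source: Section 6.1.1.3.
- Half-life: a minimum gap of 20 h is described as "more than 5 half-lives of MT-3724 in serum", so the half-life is below 20/5 = 4 h. No point value is given. I vary it from 0.5 h to just under 4 h; the lower end is my assumption.
- Model (assumed): one compartment, 1 h infusion, peak at end of infusion, peak proportional to dose. Carry-over is ignored: after more than 5 half-lives less than 0.5^5 = 3.1% of the previous dose's level remains.

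**Dose at the Day 1 end-of-infusion ECG, relative to full dose**
- Cohort 1 regimen: 10/25 = 40%.
- Cohort 2 regimen: 10/50 = 20%.

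**Exposure at each ECG, relative to the full-dose peak**
- Day 12, 2 h after end of infusion: F = 0.5^(2/t½).
- Ten minutes before end of infusion, relative to that day's own peak: E = (1 − exp(−k × 50/60)) / (1 − exp(−k)), with k = ln 2 / t½.
- Day 1 end-of-infusion ECG relative to the full-dose peak: 0.40 × E (Cohort 1) or 0.20 × E (Cohort 2).
- Highest exposure with a scheduled ECG: the larger of F and the Day 1 value.

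| t½ (h) | F: Day 12 at 2 h | E: 10 min before end of infusion | Highest now, Cohort 1 regimen | Highest now, Cohort 2 regimen |
|---|---|---|---|---|
| 0.5 | 6% | 91% | 37% | 18% |
| 1 | 25% | 88% | 35% | 25% |
| 1.5 | 40% | 86% | 40% | 40% |
| 2 | 50% | 86% | 50% | 50% |
| 3 | 63% | 85% | 63% | 63% |
| 3.99 | 71% | 85% | 71% | 71% |

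The ±10 minute window on the Day 12 recording changes little: at the longest half-life it gives 69% to 73%.

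**When the Day 12 two-hour ECG exceeds the Day 1 peak**
- Cohort 2 regimen: (50/10) × F > 1 when t½ > 2/log2(5) = 0.86 h.
- Cohort 1 regimen: (25/10) × F > 1 when t½ > 2/log2(2.5) = 1.51 h.
- At a half-life of 2 h the Day 12 exposure is 2.5 times (Cohort 2) or 1.25 times (Cohort 1) the Day 1 peak.

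**If the end-of-infusion ECG were on Day 12.** Column E applies directly to the full-dose peak. A recording taken no earlier than 10 minutes before end of infusion sits at roughly 85% to 91% of it or higher.

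**The case against.** A reader might infer that the QT/QTc objective cannot be answered at all. The documents do not support that. The objective is secondary and its wording sets no peak-exposure requirement. Day 12 supplies a predose and a two-hour triplicate at full dose in the same subject. A PK sample is due at the same two-hour point, and a footnote to Table 1-1 fixes the order when ECG and PK coincide. Adverse events are a second endpoint, and Section 9.3.3 makes the safety analyses descriptive. Section 9.3.4.2 refers exposure-response modelling to a separate plan that is not supplied, so whether it covers QTc is unknown. All of this stands.

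A reader might also infer that peak exposure at such doses was never recorded anywhere in the study. The SAP points the other way. In Parts 1 and 2, ECGs were due on Cycle 1 Day 1 at 1 h and 2 h after the start of an infusion that footnote 7 sets at about 2 h, so the second falls near end of infusion. Flat doses included 50, 75 and 100 µg/kg, and SAP Section 4.6.5 plans categorical QTcF summaries. But the infusion was longer (up to 4 h in the Part 1 Core Study), these ECGs are not described as triplicate, and they are not Part 4 data. They soften the gap without closing it.

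Nor do the documents show that the ECG timing was overlooked. Version 11 revised Table 1-1 in other respects, and its silence on ECG timing does not prove an oversight. No passage says a QT effect would track peak concentration; Section 6.1.1.1 links the peak to cytotoxicity only. The size of the gap rests on a half-life the documents do not state.

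Finally, moving the ECG removes a recording near the peak of each subject's first exposure, and a low-dose point useful for exposure-response. That is a real cost, though the Day 1 predose and two-hour ECGs remain.

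**Conclusion.** The point holds as a weakening of the objective. No scheduled ECG is taken near the full-dose peak under either step-up regimen. The highest exposure with an ECG is about 35% to 71% of that peak under the Cohort 1 regimen and about 18% to 71% under the Cohort 2 regimen. These ranges rest on the one-compartment assumptions and on assumed half-lives from 0.5 h to just under 4 h. Near the upper bound the gap is modest; at short half-lives it is large.

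A QTc change at full dose can be described two hours after infusion, with matched PK. A QTc effect at full-dose peak would be an extrapolation, and a null finding would not cover it.

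The analysis text does not close the gap. Protocol Section 9.3.3 has no ECG subsection, the synopsis offers only a change-from-baseline summary, and the supplied SAP is based on protocol version 7.0 and covers Parts 1 and 2. The primary endpoint is unaffected. This is a cheap improvement, and it concerns assessment timing only.

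**What to change.** In the ECG row of Table 1-1, move the triplicate in the last 10 minutes of infusion from Cycle 1 Day 1 to Cycle 1 Day 12, where Table 1-2 already draws PK 10 minutes before end of infusion. Keep the Day 1 predose and two-hour ECGs and the Day 12 predose and two-hour ECGs.

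This is one line in the table, with no extra visit and no change in the number of ECGs. The loss is the near-peak reading at the starter dose. If the sponsor wants to keep that reading, adding the Day 12 recording instead costs one more triplicate per subject.

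If the schedule is left as it is, state in the analysis plan for Part 4 and in the study report that the QT/QTc conclusion applies only to the exposures at which ECGs were taken.

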**Table 1-1. Schedule of Activities**

	SCR a	Treatment Period (21-day Cycles) b								EoT d	STFU e	LTFU f	Notes
		D1	D3	D5	D8	D10	D12	D15 c	D16-21				
Safety follow-up call								X					Not applicable for weekly dosing
LTFU call												X	
Local Laboratory Assessments													
Albumin		X	X	X	X	X	X						Albumin will be collected within 24 h before infusion and reviewed prior to each dose in Cycle 1 . Additional assessments of serum albumin should be made in subjects with hypoalbuminemia or other signs and symptoms of CLS as clinically indicated. See Section 6.2 for dose modification guidance for CLS.
CK		X	X	X	X	X	X						CK must be collected within 24 h before infusion in Cycle 1.
Viral serology	X												Serology for HIV, HBV, and HCV is not required if seronegativity is documented in the medical history and there are no clinical signs suggestive of HIV or hepatitis infections, or suspected exposure. Refer to Table 10-1 for specific analytes.
Urinalysis (dipstick)	X	X			X					X	X		Analysis of urine microsediment may be performed at the investigator's discretion by the local lab.
Pregnancy test		(X)								X	X		(X): performed within 72 h before dosing on D1
Central Laboratory Assessments													
Serum rituximab level (if applicable)	X												Only applicable to subjects that have received the last dose of prior RTX (Rituxan® or biosimilar) > 84 days before the start of treatment. See Section 10.2.2.4 for further details.
Hematology	X	X			X					X	X		
Chemistry	X	X			X					X	X		Includes eCrCl (see Section 10.2.2.2 ).
Coagulation	X	(X)								X			
Thyroid function	X	(X)								X			(X): Assessed D1 of every odd cycle.
HbA1c	X	(X)								X			
PK g		X	X			X							Refer to Table 1-2 for detailed time point collection.
Beta-2 microglobulin	X												
MT-3724 ADA/NAb	X	X				(X)				X	X		(X): Day 12 of Cycle 1 only

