**Table 1-1. Schedule of Activities**

	SCR a	Treatment Period (21-day Cycles) b								EoT d	STFU e	LTFU f	Notes	
		D1	D3	D5	D8	D10	D12	D15 c	D16-21					
B-cells and immunophenotype	X	X					(X)			X	X		(X): Day 12 of Cycle 1 only	
Complement	X	X								X			Should be assessed before the start of infusion and 3 hours after the start of infusion ( $\pm$ 10 min), or if a subject experiences a Grade $\geq$ 2 IRR/CLS/CRS or other hypersensitivity reaction. See Section 10.2.2.3 for details.	
Histamine	X	X								X				
Cytokines	X	X								X				
Immunoglobulins	X	X								X			Should be assessed before the start of infusion and 3 hours after the start of infusion ( $\pm$ 10 min).	
Optional tumor tissue biopsy										X			Applicable to subjects who had consented for this procedure, exhibit PD, and have accessible peripheral lymph node(s).	
Efficacy Assessments														
Radiological assessment	X	Every 6 weeks ( $\pm$ 1 week) starting from C1D1, until disease progression, death, or lost to follow-up AND For subjects without response or SD at EoT: within 7 days of the EoT Visit ( only if the previous tumor scan has been performed $>$ 4 weeks before the EoT Visit)								The investigator is encouraged to obtain the screening tumor scan as close as possible to the start of treatment. The original schedule needs to be maintained even if there is a delay in dosing. Subjects who continue to receive treatment beyond progression should also have repeat scans.				
EQ-5D	X	(X)								X	X		(X): Collected D1 of every even cycle (C2, C4, C6, etc)	
Study Treatment														
Premedication		X	X	X	X	X	X	(X)					Administered within 60 minutes prior to MT-3724 infusion. Refer to Section 6.1.2 for guidance. (X): Only when weekly dosing is implemented.	
MT-3724 infusion (TIW)		X	X	X	X	X	X						The first 3 doses of Cycle 1 must be administered at least 2 days (approx. 48 hours) apart. All subsequent doses must be given within $\pm$ 1 day of scheduled visit. All 6 doses must be given within the first 16 days, the doses should be at least 20 hours apart, and should not be administered on more than 2 consecutive days.	
MT-3724 infusion (weekly schedule) h		X			X			X					Starting with Cycle 3, doses will be administered weekly. Doses must be given within $\pm$ 2 day of scheduled visit.	

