ABC = activated B-cell; ADA = anti-drug antibodies; AE = adverse event; BMI = body-mass index; BP = blood pressure; C = cycle; CAR-T = chimeric antigen receptor T-cell therapy; CLS = capillary leak syndrome; CK = creatine phosphokinase; CRS = cytokine release syndrome; CT = computerized tomography; D = day; ECG = electrocardiogram; ECHO = echocardiogram; ECOG = Eastern Cooperative Oncology Group; eCrCl = estimated creatinine clearance; eCRF = electronic case report form; EOI = end of infusion; EoT = end of treatment; EQ-5D = EuroQol Group Quality of Life – 5-dimensions; GCB = germinal center B cell; HbA1c = glycated hemoglobin; HBV = hepatitis B virus; HCV = hepatitis C virus; HIV = human immunodeficiency syndrome; LTFU = long-term follow-up; NHL = non-Hodgkin's lymphoma; HR = heart rate; IRR = infusion-related reaction; LVEF = left ventricular ejection fraction; MRI = magnetic resonance imaging; MUGA = multigated acquisition; NAb = neutralizing antibody; NYHA = New York Heart Association; OTC = over-the-counter; PD = progressive disease; PK = pharmacokinetic; RNA = ribonucleic acid; RR = respiratory rate; SCR = screening; SCT = stem cell transplant; SD = stable disease; STFU = short-term follow-up; TIW = three times a week.

- a The screening period is up to 35 days prior to enrollment. All local/central laboratory safety assessments and radiological assessments must be collected within 28 days prior to enrollment.
- b All assessments are performed any time before dosing unless otherwise indicated. Predose assessments may be performed up to 1 day prior to dosing (except for cytokines/immunoglobulins/complement/histamine which should be collected just prior to dosing).
- c The Day 15 visit is applicable for subjects receiving the weekly dosing schedule.
- d Upon discontinuation of treatment, as soon as possible (up to 14 days) after the last dose, and before the start of new therapy.
- e A STFU visit occurs 30 days ( $\pm$  3 days) after the last dose. The STFU visit can be done via a clinic visit (recommended) or via a telephone call (if subject cannot attend a clinic visit or has started a new anticancer treatment or a new NHL treatment). If performed via a telephone call, only AEs and concomitant medications will be collected.

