**Table 6-4. MT-3724 Dose Modification Guidance and Specific Management of Toxicities**

	Specific Management	MT-3724 Dose Modificationa

Grade <math>\geq</math> 2 CLS: As defined in CTCAE v5.0, or if at least 2 of the following within the same cycle (unless unequivocally related to underlying condition) reaches the level of Grade 2:
 
 
• Hypoalbuminemia
 
• Hypotension
 
• Edema (peripheral or central, all types) and/or weight gain
 
	
Subjects should be closely monitored for signs of CLS. This includes:
 
 
• Monitoring of vital signs (temperature, heart rate, BP, respiration rate), body weight, edema of any type including both peripheral edema and central edema (such as pleural effusion or signs of dyspnea).
 
• Monitoring of laboratory parameters including hemoconcentration (eg, hematocrit, Hb), and especially albumin and CK in case of clinical symptoms indicative of CLS.
 
 
Investigators should consider supportive measures while on trial regardless of dosing or timing of dosing. If a subject experiences Grade 2 hypotension, orthostasis, edema, or hypoalbuminemia, normal saline and/or an albumin infusion may be given, as needed.
	
Treatment modification due to CLS:
 
 
• For Grade <math>\geq</math> 3 CLS, the MT-3724 treatment must be permanently discontinued.
 
• For Grade 2 CLS, the MT-3724 treatment must be held, and may only be restarted after: 
 
◦ a minimum of 7 days has elapsed after onset of CLS, and
 
◦ all signs and symptoms of CLS have resolved to at least grade 1, and
 
◦ albumin has remained <math>\geq</math> 3.0 g/dL for at least 5 days post last albumin infusion (if required) without additional albumin substitution
 
 
 
 
Subsequent doses of MT-3724 must be:
 
 
• reduced by at least 25%, and
 
• administered once weekly
 
 
or subject may be permanently discontinued at the investigator's discretion.

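### The 24 h albumin window in Cycle 1 is longer than the 20 h minimum dose spacing, so in a narrow permitted case the release sample can predate the previous infusion

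*Protocol*

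**What the plan says.** **Albumin timing.** In protocol Table 1-1 the local albumin row has an entry on each of the six Cycle 1 dosing days. Its note begins "Albumin will be collected within 24 h before infusion and", then calls for review before each dose of that cycle. Footnote b to the same table adds: "Predose assessments may be performed up to 1 day prior to dosing". Its exceptions, to be drawn just before dosing, are cytokines, immunoglobulins, complement and histamine. Albumin is not among them.

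**Dose spacing.** For the start of Cycle 1, Table 1-1 says: "The first 3 doses of Cycle 1 must be administered at least 2 days (approx. 48 hours) apart". Later doses may move by a day either way, and "the doses should be at least 20 hours apart, and should not be administered on more than 2 consecutive days". Section 6.1.1.3 repeats the 20 h minimum and states the preference: "For Cycle 1 and 2 doses are preferably administered on Days 1, 3, 5, 8, 10, and 12".

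**Cohort 2 doses.** Section 6.1.1.2 gives 10 µg/kg for doses 1 and 2, 25 µg/kg for doses 3 and 4, and 50 µg/kg "for the remaining doses (D10, D12) of the first 21-day cycle and all doses of Cycle 2". Dose 5 is therefore the first infusion at 50 µg/kg.

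**The concern.** The pre-dose albumin is a check for capillary leak syndrome (CLS). Section 12.1 says it was added to mitigate CLS, in the amendment that followed a Grade 5 event. A check that releases the next dose should reflect the effect of the last one. Two stated rules, a 24 h look-back and a 20 h minimum interval, together allow a sample that does not.

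Dose 6 in Cohort 2 is where this matters most, because there is little redundancy. Central chemistry is scheduled on Days 1 and 8 of a cycle, so the albumin before dose 6 is the only routine one between the first 50 µg/kg infusion and the Cycle 2 Day 1 labs. If it was drawn before dose 5, a subject who continues treatment has no routine albumin after either 50 µg/kg dose of Cycle 1 until about the end of the 21-day DLT period. Section 10.3.9 makes an albumin fall of at least 0.5 g/dL from Cycle 1 Day 1 part of the CLS DLT criterion. The DLT count in six subjects decides whether Part 4 uses the Cohort 1 or the Cohort 2 regimen.

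**Working it through.** The plan gives no figure for this overlap, so there is none to reproduce. The check is interval arithmetic.

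**Inputs**
- Albumin look-back: 24 h (Table 1-1, albumin row).
- Minimum spacing from dose 4 onward: 20 h (Table 1-1, three-times-weekly infusion row; Section 6.1.1.3). Neither place says whether this runs start to start or end to start, so both are shown.
- Infusion length L: 54 to 75 min, that is 0.9 to 1.25 h (Section 6.1.1.3).
- Doses 1 to 3: about 48 h apart.

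**Formulas**, with S the start-to-start spacing:
- part of the window before the previous start = max(0, 24 − S)
- part of the window before the previous end = max(0, 24 − S + L)

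| Spacing | Before previous start | Before previous end |
|---|---|---|
| 20 h start to start (S = 20) | 24 − 20 = 4.0 h (17% of 24 h) | 4.0 + 0.9 to 4.0 + 1.25 = 4.9 to 5.25 h (20 to 22%) |
| 20 h end to start (S = 20.9 to 21.25) | 3.1 to 2.75 h (13 to 11%) | 24 − 20 = 4.0 h (17%) |
| S = 22 | 2.0 h | 2.9 to 3.25 h |
| S = 24 | 0 | 0.9 to 1.25 h, the infusion itself |
| S about 48 (doses 1 to 3) | 0 | 0 |

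**Where consecutive days are allowed.** The ±1 day window permits doses 4 and 5 on Days 8/9 or 9/10, and doses 5 and 6 on Days 10/11 or 11/12. Section 6.1.1.3 attaches ±1 day to the whole list of days. On that reading doses 3 and 4 can also fall on Days 6/7. On the preferred days the shortest gap is two days, so the overlap is zero.

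**What else must happen.** Adjacent calendar days are not enough: the spacing must be under 24 h start to start. Because each dosing visit has its own albumin entry, the site must also either draw the next dose's sample before giving the current dose or count one sample for two doses.

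**The case against.** The case against is substantial.

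- **Several unlikely choices are needed together:** leaving the preferred days, dosing on consecutive days, spacing under 24 h, and an early draw or a reused sample.
- **The natural reading is one fresh sample per dose.** Table 1-1 has an entry at each dosing visit, and Section 8.1.2 wants predose assessments done on visit days before the drug is given. This makes the case less likely. It does not bar it, because footnote b allows the work to be done a day early.
- **Other documents may set the draw time.** Section 2.2.2 refers to a CLS management guide and Section 10.2.1 to a Laboratory Manual. Neither was available, so the gap is shown only for the protocol text.
- **The known risk periods are largely covered.** Section 12.1 places CLS events within a few days of initial dosing or of re-dosing after CLS. Doses 1 to 3 are about 48 h apart. After Grade 2 CLS, Table 6-4 permits restart only once "a minimum of 7 days has elapsed after onset of CLS", and then once weekly.
- **There are backstops:** weight, predose vital signs and adverse event review at each dose, extra albumin when signs appear, and observation during and after infusions (Section 8.4). Section 2.2.2 raises suspicion of CLS on any two of three signs, so albumin is not indispensable. These are partial: footnote b's one-day allowance also reaches weight, and extra albumin depends on signs already having been noticed.

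A reader might infer that a leak after the step to 50 µg/kg would be missed, or that a DLT call and the choice of Part 4 regimen would change. The documents do not support either. Nothing in them shows that albumin would fall measurably within about 20 h of dose 5, and no DLT decision is shown to turn on it. A reader might also count the permitted day patterns and treat the share with adjacent days as a frequency. Adjacent days can be 24 h or more apart, and the documents give no expected frequencies.

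**Conclusion.** The point holds as a minor inconsistency between two stated rules. At the tightest permitted spacing, 2.75 to 4.0 h of the 24 h albumin window lies before the start of the previous infusion, depending on how the 20 h is measured and how long the infusion runs. The overlap before that start shrinks to nothing at 24 h start to start. The case cannot arise between doses 1 and 3 or on the preferred schedule.

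The conclusion assumes that no manual outside the supplied documents fixes the draw time, and that footnote b applies to albumin as written. Clinical harm is an inference. The reason to act is that the check exists for CLS, the sample before dose 6 in Cohort 2 has no routine substitute until Cycle 2 Day 1, and the correction is cheap. The point does not touch the efficacy endpoints or their analysis.

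**What to change.** Reword the note on the albumin row of Table 1-1 along these lines:

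*Cycle 1 dose 1: collect albumin within 24 h before the infusion. Cycle 1 doses 2 to 6: collect albumin within 24 h before the infusion and after completion of the previous infusion. Review the result before each dose. A sample used to release an earlier dose may not be reused.*

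A same-day draw should not be required. It would reject a sample taken the evening after the previous infusion, which already postdates that infusion. Even at 20 h start to start, the new wording leaves 20 − 1.25 = 18.75 h to 20 − 0.9 = 19.1 h in which to draw the sample and obtain the result.

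The cost is faster local laboratory turnaround when doses fall on consecutive days. No scheduled draw is added, and nothing changes on the preferred schedule. If the Laboratory Manual or the CLS management guide already requires this, the new wording only brings the protocol into line.
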